#### 5.1.1 Study Date Range and Duration

The estimated duration for the study is approximately one year from the start of the intervention period (anticipated November 2022 – November 2023, depending on all approvals and other factors outside of the control of the study team).

#### 5.1.2 Number of Study Sites

There is 1 study site for this project (Flatbush Family Health Center at NYU Langone).

### 5.2 Outcome Variables

Please see the following primary and secondary outcome variables below.

#### 5.2.1 Primary Outcome Variables

The primary outcome variable is completion of initial fecal immunochemical test (FIT) or colonoscopy at 6 months.

#### 5.2.2 Secondary and Exploratory Outcome Variables

1) Completion of colonoscopy for individuals with a positive fecal immunochemical test at 6 months.

2) Determination of factors associated with non-adherence to initial fecal immunochemical testing or colonoscopy, and to completion of colonoscopy for those with positive FIT.

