## **6.2 Assessments**

### **6.2.1 Efficacy**

We will assess the efficacy of our intervention through a statistical analysis comparing the rates of completion of a FIT test or colonoscopy in the proactive outreach group compared to the usual care group. In addition, we will perform a statistical analysis comparing the rates of completion of a colonoscopy for individuals with a positive fecal immunochemical test at 6 months in the proactive outreach group compared to the usual care group.

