### **6.3.4 Recruitment, Enrollment and Retention**

Patients will be identified for inclusion in the study via accessing the Flatbush FHC EMR (Epic) and applying the inclusion and exclusion criteria previously mentioned. We will work with DataCore to obtain an initial list of eligible patients once, at the beginning of the study. The PI and study coordinators will be the only research staff with access to the list. The list will contain the following information about the eligible patients: MRN, full name, date of birth (or age), address, phone number(s), email addresses, biological sex, race, ethnicity, height/weight (or BMI), smoking status, and primary care physician's name. Data for the patients that will not be included in the study will be deleted from the electronic list provided by DataCore at the end of the study. No information will be retained about these patients.

After the mailed intervention process is complete, data regarding colorectal cancer screening will be obtained for the control group patients. This will include whether colonoscopy, FIT, or other screening tests for colorectal cancer were completed during the study period. Approved waiver of consent and HIPAA authorization for this patient group will allow this information to be collected directly from Epic by the study team.

The primary care physicians at Flatbush FHC have been notified that their intervention group patients will be contacted directly by the study team regarding this mailed CRC screening effort. All letters from the FHC (initial and final) will contain their electronic signature. These patients will receive the Study Information Sheet as part of the initial FIT kit mailing (first contact). If they decide to opt out, only de-identified data will be retained in REDCap for audits, summaries, and reporting purposes.

Subjects in the usual care group will not be approached or notified of their enrollment in the study.

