### **6.3.6 End of Study and Follow Up**

Following the completion of the intervention period of the study, we will administer interviews to a subset of patients randomized to the proactive screening arm regarding barriers to completion of colorectal screening, perceived effectiveness of the proactive outreach screening program, and any unexpected adverse effects that the patient may have experienced. Patients receiving the intervention can participate in an interview regardless of whether or not they completed CRC screening.

The interviews will be conducted by a member of the NYULH research staff trained in qualitative interviewing techniques and will occur either over the telephone or through HIPAA-compliant WebEx sessions. The interviews will be audio recorded and transcribed, with any identifiers to be removed from the transcription records. The interviews will take about 15 minutes to complete. Recording is required for participation.

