### **6.4.3 Planned Analyses**

The intent-to-screen principle will be utilized to analyze all participants for completion of the primary outcome variable of completion of colonoscopy or FIT testing screen at 6 months. The intent-to-screen principle will also be utilized to analyze all participants for completion of the secondary outcome variable of completion of colonoscopy in patients with a positive FIT test at 6 months. Analysis will be conducted utilizing an independent two sample t-test.

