#### **6.4.3.2 Secondary Objectives Analyses**

Analysis will be conducted utilizing an independent two sample t-test.

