#### **6.4.3.3 Analysis of Subject Characteristics**

We will summarize baseline and demographic characteristics utilizing standard descriptive summaries (means and standard deviations for continuous variables such as age and percentages for categorical variables gender).

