### 7.3 Subject Privacy, Confidentiality & Data Management

The collection of personal patient information will be limited to the amount necessary to achieve the aims of the research, so that no unneeded sensitive information is being collected. Only study personnel as listed on the IRB will have access to study data. Patient identifiers that will temporarily be accessed/reviewed include name, medical record number, date of birth, phone number, address, height, weight, smoking status, and CRC screening history. Electronic study data will be stored on a securely managed (MCIT) network drive and in REDCap, with password-protected access limited to trained, authorized study personnel. It is not expected that paper documents will be generated in association with this study, however, any hard copy documents will be kept in a locked cabinet in the PI's office. Electronic data will be exported into excel file format (password protected) and utilized for data analysis. De-identified data will be sent to a biostatistician for statistical analysis.

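### The listed secondary outcome on factors associated with non-adherence has no analysis that answers it: the only secondary method stated is a two-sample t-test, and the only groups named are the two arms

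*Combined protocol and SAP*

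**What the plan says.** Two secondary outcomes are listed in the Synopsis and again in section 5.2.2. The first is colonoscopy completion after a positive FIT. The second is "Determination of factors associated with non-adherence to initial fecal immunochemical testing or colonoscopy, and to completion of colonoscopy for those with positive FIT".

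The analysis text is short. Sections 6.4.1 and 6.4.3 cover the primary outcome and "completion of the secondary outcome variable of completion of colonoscopy in patients with a positive FIT test at 6 months", which is the first secondary outcome; neither mentions the second. Section 6.4.3.2, on the secondary objectives, consists of one sentence: "Analysis will be conducted utilizing an independent two sample t-test". It names no groups, dependent variable or factors.

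Comparison groups are named only in section 6.2.1. For the primary outcome the analysis is described as "comparing the rates of completion of a FIT test or colonoscopy in the proactive outreach group compared to the usual care group", and the comparison for the first secondary outcome is likewise between arms.

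Section 6.4.3.3 summarises baseline characteristics ("means and standard deviations for continuous variables such as age and percentages for categorical variables gender"), but does not break them down by completion status. Section 6.3.4 lists variables that could serve as factors, among them age and "biological sex, race, ethnicity, height/weight (or BMI), smoking status", without calling any of them a candidate predictor.

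**The concern.** A stated outcome and its stated method do not meet. Finding factors associated with non-adherence means relating patient characteristics to whether screening was completed. A t-test of outreach against usual care relates assignment to completion. Followed to the letter, the plan delivers nothing for this outcome.

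The natural repair, comparing completers with non-completers by t-test, works only in part. It suits age or BMI and, roughly, a two-level factor such as sex. It does not suit factors with several unordered categories, such as race or ethnicity. It also pools the arms without regard to assignment, although the hypothesis in section 4.1 is that assignment changes completion.

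With the factors unnamed as well, both factors and method could be chosen after the data are seen. If four to six independent factors with no true association were each tested at 0.05, the chance of at least one false positive would be 1 − 0.95⁴ = 19% to 1 − 0.95⁶ = 26%.

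**Working it through.** The plan gives no figure to reproduce: section 6.4.2 sets the size at 100 on feasibility, with no alpha, power or effect size. The check is therefore a reading of the text, followed by a calculation of what a suitable analysis could deliver.

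**Step 1: outcome against analysis.**

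| Outcome | Where analysed | Groups named |
|---|---|---|
| Primary: FIT or colonoscopy at 6 months | 6.4.1, 6.4.3, 6.4.3.1 | Outreach v usual care (6.2.1) |
| Secondary 1: colonoscopy after positive FIT | 6.4.1, 6.4.3, 6.4.3.2 | Outreach v usual care (6.2.1) |
| Secondary 2: factors associated with non-adherence | Only by implication, in the one sentence of 6.4.3.2 | None |

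**Step 2: other sources in the plan.** Section 6.3.6 plans "interviews to a subset of patients randomized to the proactive screening arm regarding barriers to completion of colorectal screening". Section 5.3.1 expects about 7 of these, which is 7/50 = 14% of the outreach arm and no usual-care patients. Surveys appear in the Synopsis, section 4.3 and section 7.7, with no content, number or analysis given. Both sources may give context on barriers. Neither has a stated analysis, and the interviews cannot estimate associations across the 100 patients.

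**Step 3: precision of a within-arm table.** From the plan: 50 patients per arm. Assumed: a two-level factor split 25/25 within each arm, the same completion p in both levels, and three uptake scenarios. The screening rates in sections 2.1 and 3.1 are clinic-wide, so they do not give 6-month uptake among patients who are due or overdue.

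- Completers = 50 × p(outreach) + 50 × p(usual care).
- Variance of the difference within an arm: V = 2p(1 − p)/25; half-width = 1.96 × √V.
- Arm-stratified difference, equal weights: half-width = 1.96 × √[(V_outreach + V_usual)/4].

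| Uptake, outreach/usual care | Completers | Half-width, outreach | Half-width, usual care | Half-width, arm-stratified |
|---|---|---|---|---|
| 30/10% | 15 + 5 = 20 | 1.96√0.0168 = 25 points | 1.96√0.0072 = 17 | 1.96√0.0060 = 15 |
| 40/15% | 20 + 7.5 = 27.5 | 1.96√0.0192 = 27 | 1.96√0.0102 = 20 | 1.96√0.00735 = 17 |
| 50/25% | 25 + 12.5 = 37.5 | 1.96√0.0200 = 28 | 1.96√0.0150 = 24 | 1.96√0.00875 = 18 |

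A category holding 10% of patients has 5 per arm. Its expected completers are 5 × 0.30 to 5 × 0.50 = 1.5 to 2.5 under outreach, and 5 × 0.10 to 5 × 0.25 = 0.5 to 1.25 under usual care. Such categories must be collapsed.

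**Step 4: the FIT-positive part.** Assumed: 20 to 50% of the outreach arm return a FIT and 4 to 10% of those are positive. Expected FIT-positives in that arm are 50 × 0.20 × 0.04 = 0.4 to 50 × 0.50 × 0.10 = 2.5. Taking the count as binomial with n = 50 and probability 0.008 to 0.05, the chance of at most one is 94% down to 28%. Even if usual care matched outreach, the trial total would be 0.8 to 5.0. No factor analysis is possible on numbers of this order.

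**The case against.** The strongest reply is that section 6.4.3.2 does not itself say between arms. A professional biostatistician (section 7.6) could compare completers with non-completers and would use percentages for categorical variables, as section 6.4.3.3 already does at baseline. For an evenly split two-level factor, a t-test and a chi-square test agree almost always. The outcome also sits under a heading that includes exploratory outcomes, in a feasibility-sized pilot. All of this stands, and it keeps the weight of the point modest. It does not supply an analysis: no factors, groups or population are written down, and the one stated method does not cover race or ethnicity.

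Three stronger readings are tempting and are not supported.

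- *That results would hinge on arbitrary category codes.* In simulation with four equal levels and completion of 15/40/40/15%, a t-test on codes 1-2-3-4 was significant in about 2% of runs, against 71 to 73% with codes 1-3-4-2. With a graded 15/23/32/40% the order reversed, at about 57% against 12%. The effect is real, but its size and direction follow from the pattern chosen, and nothing in the plan says that unordered categories would be numbered and averaged.
- *That the factor data will be discarded.* Section 7.3 speaks of identifiers that will "temporarily be accessed/reviewed include name, medical record number, date of birth, phone number, address, height, weight, smoking status", but section 6.3.4 limits deletion to patients not included in the study, and sections 7.5 and 7.11 keep data for 10 years. The documents lean towards retention.
- *That the interview sampling contradicts the objective.* The Synopsis and section 4.3 call for a random sample, while other sections describe invitation and opt-in. Random selection of invitees followed by opt-in fits all of them; the plan is silent on the draw rather than inconsistent.

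**Conclusion.** The point holds: secondary outcome 2 is listed, but the stated secondary analysis, read with the only comparison groups the plan names, does not answer it. This rests on the text and needs no assumption. The consequence is that a listed outcome goes unreported, or is analysed by choices made after the data are seen.

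The figures in the working do depend on assumed uptake, an even factor split and assumed FIT positivity. They show what a suitable analysis could deliver: differences known to within about 15 to 18 points at best, and too few FIT-positive patients for more than description. A reader should not infer that the primary comparison is compromised; it is unaffected. The point merits a change to the plan, at the lower end of that weight.

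**What to change.** In section 6.4.3.2, for secondary outcome 2, replace the t-test with a prespecified exploratory analysis:

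- Name the baseline factors in advance from the section 6.3.4 list, for example age, sex, race and ethnicity.
- Include all randomised patients, with 6-month completion of FIT or colonoscopy as the outcome.
- Tabulate completion by each factor within arm, and give arm-stratified differences with 95% confidence intervals.
- State beforehand how sparse categories will be collapsed.
- Make no significance claims.
- For the FIT-positive part, describe each patient individually and attempt no factor analysis.

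The cost is a few sentences in section 6.4.3.2 and a modest extension of the tables already planned in section 6.4.3.3, using variables already extracted. No new data collection and no change to the primary analysis is needed. The downside is that the estimates will be imprecise and descriptive only, and the report should say so.

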### **5.3 Study Population**

Our study population includes men and women aged 45-75 who are patients in the Flatbush Family Health Center medical practice and are due or overdue for CRC screening. The patient population in the Flatbush FHC medical practice is an underserved population that currently has lower CRC screening rates compared to the average screening rate in New York State. Assessing the effectiveness of a proactive outreach CRC screening program is pivotal to develop strategies to increase CRC screening rate in underserved populations.

#### **5.3.1 Number of Participants**

There will be a total of 100 participants in the study, 50 of whom will be randomized to receive proactive screening outreach and 50 of whom will be randomized to receive usual care.

Approximately 7 patients from the intervention group are expected to complete a follow-up interview about their experience with the proactive program.

#### **5.3.2 Inclusion Criteria**

- Men and women aged 45-75
- Receiving medical care at Flatbush FHC
- Due or overdue for CRC screening

#### **5.3.3 Exclusion Criteria**

- Age younger than 45 years old or greater than 75 years old
- Up-to-date with colorectal cancer screening (FIT within 1 year or colonoscopy within 10 years)
- History of colorectal cancer, inflammatory bowel disease or colorectal polyps
- No address or phone number on file
- FIT test ordered within 6 months

#### **5.3.4 Vulnerable Populations**

We do not intend to target recruitment/enrollment of vulnerable subjects as defined by federal regulations or institutional policies.

## 6 – Methods

### 6.1 Intervention

#### 6.1.1 Description of Intervention

Our proposed intervention involves proactive outreach for CRC screening for patients receiving care at Flatbush FHC. More specifically, patients randomized to the proactive outreach group will receive a letter from their clinic (mailed by the study team) explaining colorectal cancer screening options (FIT vs colonoscopy) including a FIT kit with completion and return instructions. The letter will also include information for navigation to a screening colonoscopy instead of FIT testing, if deemed to be the patient's preference. A study information sheet will be included to inform the patient that their data will be used for this research study and explain that the screening by FIT is not a research procedure, but a standard of care screening test for which they are due or overdue.

Approximately 10-14 days after mailing the FIT kit, patients who have not completed screening will receive a telephone call (with voice message left) and text message, querying whether the FIT kit was received and reminding the patient to complete the test or request a new kit, if needed.

Finally, if the FIT kit has not been submitted after about two weeks from the reminder call/text message, the study team will mail a final letter to the patient on behalf of the clinic, reminding them to complete and return the FIT kit.

If no FIT kit is returned after an additional three weeks, there will be a final note uploaded to the patient's chart alerting the patient's primary care physician to complete further action regarding CRC screening as indicated.

Those patients with a positive FIT test result will be receive assistance with navigation to scheduling a colonoscopy by the study coordinator or appropriate clinic staff. Screening and diagnostic colonoscopy completion will be facilitated through phone calls to triage whether a colonoscopy can be scheduled over the phone or requires an in-person pre-colonoscopy visit. In addition, it will be facilitated through ensuring that bowel prep is mailed to the patient with instructions or is available for pick-up in clinic. Finally, bowel preparation instructions and appointment reminders will be performed via phone call, text or mail 5-7 days prior to colonoscopy.

After the intervention period is over, patients in the intervention group will be invited to complete a qualitative interview with a trained member of the study staff, during which they will be asked about their personal experience with the proactive outreach screening program. An invitation letter will be mailed and non-responders will receive a follow-up phone call or text message to gauge interest in participating. Those who agree will be verbally consented over the phone prior to the interview.

Patients need not have completed the at-home screening to take part in the interview. Interviews will be audio recorded and professionally transcribed, with all identifiers scrubbed from the transcription.

#### **6.1.2 Method of Assignment/Randomization**

The study biostatistician will randomize 50 eligible patients to proactive outreach and 50 eligible patients to usual care, stratified by age and biological sex. Proactive outreach patients will be blind to the presence of an alternative group assignment and "usual care" patients will be unaware of group assignment altogether.

#### **6.1.3 Selection of Instruments/Outcome Measures**

The primary outcome measure is completion of initial fecal immunochemical test (FIT) or colonoscopy at 6 months. Both colonoscopy and fecal immunochemical tests are well-validated screening modalities for colorectal cancer that have been extensively studied throughout the years.

#### **6.1.4 Intervention Administration**

Please note: all days listed beyond day 0 have a +5 day tolerance window.

Day 0: Patients randomized to the proactive outreach group will be mailed letters explaining CRC screening options and a FIT kit with detailed instructions for collection and submission.

Day 10-14: In the proactive outreach group, if a FIT kit has not been submitted by this time point, the patient will receive a call or voice message from our research team to ensure FIT kit was received and reminding the patient to complete and return it or request a new kit, if necessary.

Day 28: If the FIT kit has not been submitted, the patient will receive a final letter reminding the patient to complete and return the FIT kit.

Day 56: For patients who have still not submitted a FIT kit or requested screening via colonoscopy, there will be a final note in the chart alerting the patient's primary care physician to complete further action regarding CRC screening as indicated.

Days 7-180: Patients with a positive FIT test result will receive assistance with navigation to scheduling a follow-up colonoscopy. If patients indicated that they prefer colonoscopy to FIT testing, they will also receive assistance with navigation to scheduling a colonoscopy. Assistance to scheduling a colonoscopy will include an initial phone call performed by our research coordinator or appropriate clinic staff to triage whether a colonoscopy can be scheduled over the phone or requires an in-person pre-colonoscopy visit. In addition, study staff will ensure bowel prep will either be mailed to the patient with instructions or made available to pick-up in clinic, depending on patient preference. Finally, bowel preparation instructions and appointment

reminders will be performed via phone call, text or mail 5-7 days prior to scheduled colonoscopy.

### **6.1.5 Reaction Management**

Patients will be made aware in their testing instructions that the presence of a positive FIT test result does not confirm the presence of colorectal cancer. The patient will be able to follow-up with appropriate clinic staff, as well as with a gastroenterologist at the time of their colonoscopy in order to further answer any questions.

## **6.2 Assessments**

### **6.2.1 Efficacy**

We will assess the efficacy of our intervention through a statistical analysis comparing the rates of completion of a FIT test or colonoscopy in the proactive outreach group compared to the usual care group. In addition, we will perform a statistical analysis comparing the rates of completion of a colonoscopy for individuals with a positive fecal immunochemical test at 6 months in the proactive outreach group compared to the usual care group.

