## **Secondary and Exploratory Outcome Variables**

Secondary outcome variables include:

- 1) Completion of colonoscopy for individuals with a positive fecal immunochemical test at 6 months.
- 2) Determination of factors associated with non-adherence to initial fecal immunochemical testing or colonoscopy, and to completion of colonoscopy for those with positive FIT.

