## 5 - Study Design

### 5.1 General Design Description

Our study is a single-site randomized, compared effectiveness study. Patients randomized to the proactive outreach group will be blind to the presence of an alternative group assignment. Patients randomized to the usual care group will be blind to the presence of group assignment altogether. Group allocation will be concealed because all patients will be randomized at a single time point. To accurately assess whether this proactive approach is effective, real-world, unbiased behavior by the patients involved is vital. Intervention group patients will be informed that their data will be used for this research project via a study information sheet included with the initial FIT kit mailing. This sheet will clearly indicate that the CRC screening itself is standard of care screening for which they are due and not a research test. We are seeking a waiver of HIPAA authorization, a complete waiver of consent for the usual care group, and a waiver of documentation of written consent for the intervention group, including the subset of intervention patients who complete the post-intervention interview. This subset will be verbally consented via telephone prior to completing the interview.

The study team will operate mainly in the background, to facilitate mailings and reminders. All materials will be sent on behalf of the clinic, using the clinic's usual stationery, and containing the electronic signature of the patient's primary care physician, when applicable. The study team will be tracking the cost and effort involved to help the clinic determine the feasibility of long-term implementation of a proactive screening program for CRC.

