## **6.4 Statistical Method**

### **6.4.1 Statistical Design**

The intent-to-screen principle will be utilized to analyze all participants for completion of the primary outcome variable of completion of colonoscopy or FIT testing screen at 6 months. The intent-to-screen principle will also be utilized to analyze all participants for completion of the secondary outcome variable of completion of colonoscopy in patients with a positive FIT test at 6 months. Analysis will be conducted utilizing an independent two sample t-test.

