### 7.5 Data Collection

Data will be collected at the beginning the study during the initial eligibility screening process as well as ongoing throughout the intervention period in order to ascertain FIT testing and/or colonoscopy completion results. Data will only be accessed by trained, authorized study personnel. Data will be retained for the next 10 years for use in future studies following the completion of this pilot study.

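### The between-arm t-test on colonoscopy after a positive FIT cannot validly estimate the intervention's effect on follow-up, and the sections giving its denominator need reconciling.

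*Combined protocol and SAP*

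**What the plan says.** The synopsis and section 5.2.2 define the first secondary outcome as "Completion of colonoscopy for individuals with a positive fecal immunochemical test at 6 months". Section 6.2.1 turns it into a between-arm comparison, "comparing the rates of completion of a colonoscopy for individuals with a positive fecal immunochemical test at 6 months in the proactive outreach group" against usual care. These three places restrict the outcome to people with a positive FIT.

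Sections 6.4.1 and 6.4.3 apply the intent-to-screen principle to "analyze all participants for completion of the secondary outcome variable of completion of colonoscopy in patients with a positive FIT test at 6 months". That sentence starts from everyone randomised and ends with FIT-positives. Section 6.3.7 adds that the number mailed a kit, 50, remains the denominator for the rest of the study, and does not limit this to the primary outcome.

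The test is the same throughout. Section 6.4.3.2 reads "Analysis will be conducted utilizing an independent two sample t-test", and 6.4.1 and 6.4.3 repeat it.

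Two design facts matter. Under 6.1.4, "Patients randomized to the proactive outreach group will be mailed letters explaining CRC screening options and a FIT kit with detailed instructions"; usual care gets no mailing. And 6.4.2 bases the 100 participants on feasibility, with no expected number of positive FITs.

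**The concern.** Follow-up after a positive FIT shows whether the navigation component works, so a reader will take a between-arm difference here as evidence about navigation. The plan leaves two denominators open, and each gives a different quantity.

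If only FIT-positives are counted, the groups compared are not the groups randomised. The mailing changes who takes a FIT and therefore who can test positive. Those who respond to a mailed kit may differ from those tested in a clinic visit in ways that also affect whether they go on to colonoscopy. The groups will also be very small.

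If all 50 per arm are counted, randomisation is kept, but the rate rises whenever more people take a FIT, whatever happens afterwards. Section 6.2.1 would present that rate as colonoscopy completion among FIT-positives. Two analysts following the text could report different rates, and neither could attribute a difference to better follow-up.

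**Working it through.** The plan gives no power calculation or expected count to reproduce. Only 50 + 50 = 100 can be checked, and it agrees.

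**Inputs.** From the documents: 50 per arm, kits mailed to outreach only, two-sample t-test. Assumed, because the documents give no such rates: FIT uptake 30, 40 or 50% in outreach and 10, 15 or 20% in usual care; positivity 5, 7.5 or 10%; colonoscopy completion 80% versus 50% of positives unless stated otherwise. A favourable case outside this grid takes uptake of 60% versus 30% and positivity of 10%.

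**FIT-positive reading.** Positives per arm follow Binomial(50, q) with q = uptake × positivity. A pooled t-test needs at least one positive in each arm and three in total, so it fails on group size when an arm is empty or the split is 1 versus 1. It also fails if every outcome within each arm is the same, because the pooled variance is then zero.

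Midpoint (40% vs 15%, 7.5%):
- Expected positives: 50 × 0.40 × 0.075 = 1.5, and 50 × 0.15 × 0.075 = 0.56.
- P(none): 0.97^50 = 0.218 in outreach, and 0.98875^50 = 0.568 in usual care.
- P(at least one empty arm): 1 − (1 − 0.218)(1 − 0.568) = 0.662.
- P(1 versus 1): 0.337 × 0.323 = 0.109.
- Not computable on group size: 0.662 + 0.109 = 0.771. With zero variance added: 0.886.

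| | Grid range | Midpoint | Favourable |
|---|---|---|---|
| Expected positives, outreach | 0.75–2.5 | 1.5 | 3.0 |
| Expected positives, usual care | 0.25–1.0 | 0.56 | 1.5 |
| At least one empty arm | 41–88% | 66% | 25% |
| Not computable, group size | 49–95% | 77% | 30% |
| Not computable, with zero variance | 69–98% | 89% | 53% |

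With 50% completion in both arms, the last row's grid range is 61–97%. The pooled form is the generous choice: an unequal-variance t-test needs two positives in each arm, which has probability 36% even in the favourable case. Where a comparison can be made, it says little. With 3 versus 1 or 3 versus 2 positives, complete separation gives a Fisher exact p of 0.25 or 0.10.

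**All-50 reading.** Expected rate = uptake × positivity × follow-up. At the midpoint with the same 70% follow-up in both arms:
- Outreach: 0.40 × 0.075 × 0.70 = 2.1%.
- Usual care: 0.15 × 0.075 × 0.70 = 0.79%.

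The ratio, 0.40 / 0.15 = 2.67, comes entirely from uptake. If follow-up were worse in outreach (50% versus 80%):
- Outreach: 0.40 × 0.075 × 0.50 = 1.5%.
- Usual care: 0.15 × 0.075 × 0.80 = 0.9%.

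The arm with worse follow-up would still show the higher rate. Significance would be rare: with identical 70% follow-up, the all-50 t-test reaches p < 0.05 in 0.2–6.9% over the grid.

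**The case against.** The strongest reply is that the denominator is hardly in doubt. Three places restrict the outcome to FIT-positives, and the sentence in 6.4.1 and 6.4.3 ends the same way. It can be read as analysing every FIT-positive participant in the arm assigned. That is the more natural reading, and it stands. But 6.3.7 states a denominator of 50 for the rest of the study without limiting it, so the sections still need reconciling.

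A reader might infer that the t-test does not measure follow-up at all. That goes too far. Among FIT-positives it does compare two follow-up proportions, and each describes its own arm. What fails is reading the difference as an effect of the intervention. Nor is the test never computable: in the favourable case group size allows it in 70% of trials, and 47% remain after zero variance is counted.

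A reader might also infer that usual-care FIT results will not be collected, because 6.3.4 says "This will include whether colonoscopy, FIT, or other screening tests for colorectal cancer were completed during the study period". The documents do not support that either. Section 7.5 plans collection "ongoing throughout the intervention period in order to ascertain FIT testing and/or colonoscopy completion results", and 7.7 includes FIT results in the study records. Section 6.3.4 simply does not name the result.

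Finally, this is one secondary outcome in a pilot sized on feasibility, and every rate above is assumed. That limits the weight of the point. It does not justify the test, and feasibility aims favour a descriptive report. The conflict between sections and the selection after randomisation need no assumed rate.

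**Conclusion.** The point holds and should be corrected before analysis. The planned between-arm t-test cannot validly estimate the intervention's effect on follow-up under either denominator. Among FIT-positives the comparison is not randomised and is often not computable. Over all 50 per arm it is randomised and valid for the outcome *FIT-positive and colonoscopy completed*, but it must not be labelled follow-up. The percentages depend on the assumed uptake, positivity and completion rates; the structural argument does not.

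The harm is a mislabelled or missing estimate, not frequent false significance. The primary outcome, completion of FIT or colonoscopy at 6 months, is not affected.

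It is also tempting to assume that the 6-month window runs from one shared day 0. The documents do not say so. Section 6.1.4 ties day 0 to the outreach mailing; 5.1 says only that "Group allocation will be concealed because all patients will be randomized at a single time point"; and 6.3.7 allows later replacements in both arms.

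**What to change.** - **Sections 6.2.1, 6.4.1, 6.4.3 and 6.4.3.2:** state that the denominator for this outcome is patients with a positive FIT, analysed in the arm to which they were randomised. Replace the between-arm t-test with counts per arm (x of y) and exact 95% confidence intervals, labelled descriptive.
- **Section 6.3.7:** limit the denominator of 50 to the primary outcome.
- **Section 6.3.4:** name the FIT result among the data extracted for control patients.

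Optional additions are an all-randomised comparison labelled *FIT-positive and colonoscopy completed*; a stated start date for the 6-month window in both arms, including replacements, which would be a new rule; and a listing of FIT and colonoscopy dates.

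The cost is wording in six sections and the IRB amendment required by 7.2 and the section on study modification. Sample size, schedule and primary analysis do not change. The downside is that the secondary comparison becomes descriptive, with very wide intervals: 2.5–100% for 1 of 1, 16–100% for 2 of 2, and 9–99% for 2 of 3. That width shows how little so few positives can say.
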